8.3 Endpoints

8.3.1 *Primary Endpoint(s)*

The primary objective (to assess the safety and tolerability of BMS-986183 administered as monotherapy and in combination with nivolumab in subjects with HCC) will be measured by the

primary endpoint(s) of incidence of AEs at its worst grade, SAEs at its worst grade, AEs leading to discontinuations, deaths, and frequency of laboratory test toxicity grade shifting from baseline. Safety will be evaluated as described in Table 5.1-1.

8.3.2 Secondary Endpoint(s)

The first secondary objective (to assess the preliminary anti-tumor activity of BMS-986183 administered as monotherapy and in combination with nivolumab as measured by ORR, response duration, and PFS) will be measured by the following secondary endpoints:

- Best overall response (BOR): defined as the best response designation over the study as a whole, recorded between the dates of first dose until the last tumor assessment prior to subsequent therapy. CR or PR determinations included in the BOR assessment must be confirmed by a second scan performed no less than 4 weeks after the criteria for response are first met. For those subjects who have surgical resection, only presurgical tumor assessments will be considered in the determination of BOR.
- ORR: defined as the total number of subjects whose BOR is either a CR or PR divided by the total number of subjects in the population of interest.
- Duration of response (DoR): defined as the time between the date of first response and the subsequent date of objectively documented disease progression or death, whichever occurs first. For those subjects who remain alive and have not progressed or received subsequent therapy, DoR will be censored on the date of last tumor assessment
- PFS: defined as the time from the first dose of study drug to the date of the first objective documentation of tumor progression or death due to any cause. Subjects who did not progress nor died will be censored on the date of their last tumor assessment. Subjects who did not have any on-study tumor assessments will be censored on the date of the first dose of study drug. Subjects who started any subsequent anti-cancer therapy without a prior reported progression will be censored at the last tumor assessment prior to initiation of the subsequent anti-cancer therapy. Subsequent anti-cancer therapy will be defined as the following therapy, which started after the treatment start date: systemic anti-cancer/anti-neoplastic therapy, any investigational drug, or palliative local therapy.
- PFS rate at week 't': defined as the proportion of subjects who remain progression free and surviving at 't' weeks (t=12, 24, 36, etc). The proportion will be calculated by the product-limit method (Kaplan-Meier [K-M] estimate) which takes into account censored data.
- The second secondary objective (to characterize the PK of the total antibody [unconjugated antibody + antibody conjugated to tubulysin or antibody conjugated to any tubulysin metabolites], active ADC [antibody conjugated to tubulysin], and unconjugated tubulysin) of BMS-986183 as monotherapy and in combination with nivolumab will be measured by the following secondary endpoints, when applicable (see Section 5.5 for details):
- Cmax
- Tmax
- AUC(0-T)
- AUC(TAU)
- Ctau

- Ctrough
- CLT
- Vss
- Vz
- AI_Cmax
- AI_Ctau
- AI_AUC(TAU)
- Css,avg
- T-HALF

The third secondary objective (To assess the effect of dosage regimen and exposure [active ADC and unconjugated tubulysin] of BMS-986183 as monotherapy on the QT interval) will be measured by the following secondary endpoints:

• Changes in QTcF (Δ QTcF) from baseline, at selected times

The fourth secondary objective (to characterize the immunogenicity of BMS-986183 as monotherapy and in combination with nivolumab) will be measured by the following secondary endpoints:

• The endpoints of immunogenicity of BMS-986183 as monotherapy and in combination with nivolumab include frequency of different subject immunogenicity status, eg, subject positive ADA, persistent positive ADA and others. Definitions of all the immunogenicity endpoints will be provided in the SAP.

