Retreatment may be allowed in BMS-986183 and nivolumab dose escalation (Part 3) and BMS-986183 and nivolumab dose expansion (Part 4) of this study for subjects with disease progression during follow-up. Subjects who complete approximately 1 year (17 cycles, with 21 days/cycle) of study therapy and who enter survival follow-up with ongoing disease control (CR, PR, or SD) for reasons other than drug-related toxicity may be eligible for retreatment, upon subsequent confirmed disease progression within 12 months of the last dose of study drug (on a case-by-case basis) after careful evaluation and discussion with the BMS Medical Monitor to determine whether the benefit/risk ratio supports administration of further study therapy. Subjects meeting criteria for retreatment will be treated up to approximately 1 year (17 cycles, with 21 days/cycle) with the originally assigned dose regimen (eg, same dose and dose schedule administered during the first approximately 1 year [17 cycles, with 21 days/cycle]) or modified dose regimen, unless that dose and schedule were subsequently found to exceed the MTD, in which case the subject will be treated at the next lower or alternate dose and schedule. Subjects entering this phase will follow the schedule as outlined in Table 5.1-3. Samples for PK will be collected less frequently (Table 5.5.1-3).

Response Follow-up Period

Subjects with SD, PR, or CR at study drug discontinuation will continue to have radiologic and clinical tumor assessments at least every 3 to 4 months during the survival follow-up period (Section 3.1) until progression, death, or initiation of new treatment (whichever occurs first).

Radiological tumor assessments for subjects who have ongoing clinical benefit may continue to be collected after subjects complete the survival follow-up period of the study. Subjects who have disease progression following treatment with study drug will not be evaluated for response beyond the EOT visit and will be allowed to receive other tumor-directed therapy as required.

3.1.1 Dose Escalation (BMS-986183 Dose Escalation [Part 1] and BMS-986183 and Nivolumab Dose Escalation [Part 3])

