4.5.7 Treatment Beyond Disease Progression in BMS-986183 and Nivolumab Combination Therapy

Accumulating evidence indicates a minority of subjects treated with immunotherapy may derive clinical benefit despite initial evidence of PD.⁴⁶

Subjects treated with BMS-986183 and nivolumab combination therapy may be permitted to continue combination therapy beyond initial RECIST v1.1-defined PD, as assessed by the investigator, as long as they meet the following criteria:

- Investigator-assessed clinical benefit
- Tolerance of study drug
- Stable performance status

- Treatment beyond progression will not delay an imminent intervention to prevent serious complications of disease progression (eg, central nervous system [CNS] metastases).
- Subject provides written informed consent prior to receiving additional combination treatment. All other elements of the main consent including description of reasonably foreseeable risks or discomforts, or other alternative treatment options will still apply.

A radiographic assessment/scan should be performed within 6 weeks of initial investigatorassessed progression to determine whether there has been a decrease in the tumor size or continued PD. The assessment of clinical benefit should be balanced by clinical judgment as to whether the subject is clinically deteriorating and unlikely to receive any benefit from continued treatment with combination therapy.

If the investigator deems that the subject continues to achieve clinical benefit by continuing treatment, the subject should remain on the study and continue to receive monitoring according to the Table 5.1-2.

Discontinuation due to Further Progression (Confirmed Progression)

For the subjects who continue combination therapy beyond progression, further progression is defined as an additional 10% increase in tumor burden with a minimum 5 mm absolute increase from time of initial PD. This includes an increase in the sum of diameters of all target lesions and/or the diameters of new measurable lesions compared to the time of initial PD. Combination therapy should be discontinued permanently upon documentation of further progression.

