Nivolumab Administration	x			X					X					For BMS-986183 and nivolumab dose escalation (Part 3) and BMS-986183 and nivolumab dose

Procedure ^a	C2	2 and	C3		C4					ЕОТ	Follow- up (30 and 60 Days After Last Dose)	Follow- up (100 Days After Last Dose) ^c	Survival Follow-up ^d	Notes
	D1	D8	D15	D1	D2	D4 ^e	D8	D15	D1		(± 5 days)	(± 10 days)	(± 2 weeks)	
														expansion (Part 4) only. BMS-986183 is infused first followed by nivolumab. See Section 4 for administration details. See Section 3.1.1.2 for observation times. The start and stop time of the study drug infusion should be documented (start of drug infusion = 0 hour).
Other														
Other Anti-cancer Therapies													x ^j	
Subject Status													X	Also see tumor assessment schedule above

^a In the event that multiple procedures are required at a single timepoint, the ECG may be obtained up to 15 minutes earlier, vital signs may be obtained up to 10 minutes earlier or later, and clinical laboratory sample may be obtained up to 5 minutes earlier than the nominal PK timepoint, ensuring the PK samples can be collected on time.

^b Individual subjects with SD or PR may have 6 months (9 cycles, with 21 days/cycle) of extended treatment with BMS-986183 after the first treatment period (17 cycles, with 21 days/cycle) on a case-by-case basis after specific consultation and agreement between the investigator and BMS medical monitor. These subjects, as well as any subjects in BMS-986183 and nivolumab dose escalation (Part 3) or BMS-986183 and nivolumab dose expansion (Part 4) who meet the criteria to continue combination therapy beyond progression (see Section 4.5.7), will follow the assessment/procedure schedule for C5 to C17 subjects.

^c BMS-986183 and nivolumab dose escalation (Part 3) and BMS-986183 and nivolumab dose expansion (Part 4) only.

^d For all subjects, subject status will be assessed by telephone contact, office visit, or documented clinic visit every 12 weeks (± 2 weeks) up to 6 months from his or her last dose of study drug.

^e C4D4: ± 1 day.

f

Vital signs will be obtained before the BMS-986183 infusion and then every 30 minutes (\pm 10 minutes) until 30 minutes following completion of the last infusion. If any vital sign is abnormal at the final check, the subject must be observed further for a period of time, as clinically indicated. The start and stop time of the study drug infusion should be documented (start of drug infusion = 0 hour).

^g Only anti-cancer treatments.

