4.2 Secondary Endpoints

4.2.1 Efficacy Endpoints

Efficacy endpoints that are based on tumor response data will be derived per RECIST v1.1 response criteria.

- **Best overall response (BOR)**, defined as the best response designation over the study as a whole, and recorded between the date of first dose until the last tumor assessment prior to subsequent anticancer therapy and the date of first objectively documented progression per RECIST v1.1, whichever occurs first. CR or PR determinations included in the BOR assessment must be confirmed by a second scan performed no less than 4 weeks after the criteria for response are first met. For those subjects who have surgical resection, only pre-surgical tumor assessments will be considered in the determination of BOR.
- **Objective Response Rate (ORR)**, defined as the total number of subjects whose BOR is either a CR or PR divided by the total number of subjects in the population of interest.
- **Duration of Response (DOR)**, defined as the time between the date of first response and the subsequent date of objectively documented disease progression or death, whichever occurs first. For those subjects who remain alive and have not progressed or received subsequent anticancer therapy, duration of response will be censored on the date of last tumor assessment. For subjects who received subsequent anticancer therapy, duration of response will be censored on the date of last tumor assessment prior to initiation of subsequent anticancer therapy. Response duration will only be evaluated in participants with a BOR of CR or PR.

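### A response first seen after progression counts toward ORR under Protocol 8.3.2 but not under SAP 4.2.1

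*Protocol*

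**What the plan says.** Protocol Section 8.3.2 defines BOR across the whole study, "recorded between the dates of first dose until the last tumor assessment prior to subsequent therapy". Progression does not close that window. SAP Section 4.2.1 starts from the same idea but ends the window at "the last tumor assessment prior to subsequent anticancer therapy and the date of first objectively documented progression per RECIST v1.1, whichever occurs first".

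Both documents then define ORR identically, "defined as the total number of subjects whose BOR is either a CR or PR divided by the total number of subjects in the population", so ORR inherits whichever BOR window is used.

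The protocol provides two routes in Parts 3 and 4 by which a subject can be dosed and scanned after progression:

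- **Treatment beyond progression (Section 4.5.7).** Combination subjects "may be permitted to continue combination therapy beyond initial RECIST v1.1-defined PD, as assessed by the investigator". Under a footnote to the Section 5.1 schedule, subjects "who meet the criteria to continue combination therapy beyond progression (see Section 4.5.7), will follow the assessment/procedure schedule for C5 to C17 subjects".
- **Retreatment (Section 3.1).** Subjects who finish about a year of therapy with disease control "may be eligible for retreatment, upon subsequent confirmed disease progression within 12 months of the last dose of study drug".

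**The concern.** Under one current document a subject who progresses and later responds on continued combination therapy is a responder. Under the other the same subject is not. The protocol reading also conflicts with the protocol's own PFS definition: the subject would count as a response in ORR after PFS had already recorded progression.

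ORR is a secondary endpoint, but it carries the precision and error-rate justification for the 50 subjects in Part 4. The study is open-label, so if the rule is settled after responses are known, the ORR could be chosen with the data in view.

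**Working it through.** **1. The two windows side by side**

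| | Protocol 8.3.2 | SAP 4.2.1 |
|---|---|---|
| Start | First dose | First dose |
| Closes at subsequent therapy | Yes | Yes |
| Closes at first RECIST v1.1 progression | No | Yes, if earlier |
| Confirmation at 4 weeks or more | Required | Required |

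**2. Will scans exist after progression?** Yes, for treatment beyond progression. Protocol 4.5.7 asks for a scan within 6 weeks of initial progression. The C5 to C17 schedule that these subjects then follow has tumor assessments every 6 weeks.

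**3. Can such a scan be a RECIST response?** Yes, in a limited case. In Appendix 6, progression is measured from the smallest sum on study and PR from the baseline sum. Let B be the baseline sum and suppose it is also the smallest. Target-lesion growth to 1.2 × B, with at least 5 mm absolute increase, is PD. A later fall to 0.7 × B or less, with no new lesions and no nontarget progression, meets the PR criteria at that timepoint. If it is confirmed at least 4 weeks later, the subject has a BOR of PR under the protocol window. Under the SAP window that scan is never considered.

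**4. Which routes are affected?**

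- *Treatment beyond progression, Parts 3 and 4:* direct conflict.
- *Retreatment, Parts 3 and 4:* undetermined. The protocol window closes at subsequent therapy. The list of such therapies in 8.3.2 (given under PFS) takes in investigational drugs and does not say whether study drug is excluded. If retreatment counts, the protocol window also closes first and there is no conflict. If it does not count, only subjects who entered follow-up with SD could change status, because those with a confirmed CR or PR are already responders under both documents.
- *Part 2 combination extension:* no conflict. Protocol 3.1.2.1 limits the main analysis to the period up to and including progression.
- *Monotherapy otherwise:* progression ends treatment (Protocol 3.5 and 4.5.6).

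**5. Size.** The Part 4 figures in Protocol 8.1.2 reproduce as exact binomial tails with n = 50:

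| True ORR | P(X ≥ 10) | P(X ≥ 11) | Stated |
|---|---|---|---|
| 30% | 0.9598 | 0.9211 | 96%, 92% |
| 15% | 0.2089 | 0.1199 | 21%, 12% |

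They do not depend on which BOR window is meant, because they take the true ORR as given.

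The effect of the window on the estimate is 1/50 = 2 percentage points per subject who responds only after progression. For example, 9 responders before progression give 9/50 = 18%, and one more after progression gives 10/50 = 20% under the protocol and leaves 18% under the SAP.

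**The case against.** The best defence is that the SAP already holds the proper cut-off and can be read as refining a looser protocol sentence. Protocol 4.5.7 points the same way: its further-progression criteria serve subject management, and efficacy follows RECIST v1.1. This makes the intended analysis fairly clear, but it does not reconcile the texts. Naming RECIST v1.1 sets the criteria for each scan, not the date on which the BOR window closes.

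Second, Appendix 6 refers to Table 4.3-1 for BOR when confirmation is required, and to the full RECIST publication. Neither was available for this review, so a limit stated there cannot be excluded. The 8.3.2 definition as worded still has none.

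Third, the affected group is narrow. Any timepoint with new lesions is PD, PR is judged against the original baseline, and confirmation is needed. Protocol 3.1 also says that subjects who progress following treatment are not evaluated for response beyond the end-of-treatment visit. That narrows the follow-up cases, although the retreatment schedule does list scans, and it does not reach subjects still on treatment beyond progression. These points limit the size and leave the contradiction in place.

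Fourth, ORR is secondary and no formal testing is planned. That also stands, and it limits the weight of the point.

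**Conclusion.** The protocol and SAP give different BOR windows, and in Parts 3 and 4 they can classify the same subject differently for ORR. The protocol wording is the one to change. The conflict is established for treatment beyond progression and conditional for retreatment. The number of subjects is probably small, and each moves a 50-subject ORR by 2 points.

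Two stronger readings are tempting, and the documents do not support them.

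- *That the Part 4 false-positive rates are understated.* Adding an assumed 3 or 5 points to the 15% rate gives tails of 41% and 28%, or 56% and 42%, for at least 10 and at least 11 responses. The arithmetic is right, but nothing in the documents supports those increments. The protocol states its rates for a true ORR of 15%. If that 15% is on the protocol definition, it already includes any post-progression responders, and 21% and 12% stand. Inflation would need a 15% set on the SAP definition with counting on the protocol definition, which neither document says. Nor are 10 and 11 responses stated as decision thresholds for Part 4.
- *That retreatment responses definitely enter the protocol ORR.* This depends on whether study-drug retreatment is subsequent therapy, which is not stated.

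**What to change.** 1. In Protocol 8.3.2, close the BOR window at the earlier of first documented RECIST v1.1 progression and subsequent anticancer therapy, matching SAP 4.2.1.
2. In both documents, state whether retreatment with study drug counts as subsequent therapy.
3. Report responses first seen after progression separately from ORR, using the treated-beyond-progression population that SAP 6.3 already defines. As worded, that population covers anyone given nivolumab after initial progression, so retreated and Part 2 extension subjects should be shown apart from those who simply continued combination therapy.

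The cost is a sentence or two in each document and one supplementary table. Visits, scans and dosing do not change. The downside is that ORR may be slightly lower than under the present protocol wording.

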8.4 Analyses

8.4.1 Demographics and Baseline Characteristics

Frequency distributions of gender and race will be tabulated. Summary statistics for age, body weight, height, and Body Mass Index will be tabulated.

8.4.2 Efficacy Analyses

Efficacy results will be presented by dose and regimen. Individual BOR, DoR, and PFS will be listed using RECIST v1.1 criteria (Appendix 6).⁸¹ BOR outcomes will be tabulated by dose and dose regimen. The ORR and PFS rates (eg, at 24 weeks) and the CI will be provided by dose and dose regimen if there is enough data. The DoR and PFS will be estimated by K-M methodology, PFS rates (eg, at 24 weeks) will be similarly estimated, based on K-M methodology. Individual changes in the tumor burden over time will be presented graphically by dose. OS may also be assessed as part of exploratory efficacy analysis, by K-M plots and medians and OS rates at specified times, and by tabulation, graphics, and/or medians as appropriate for the endpoints.

8.4.3 Safety Analyses

All recorded AEs will be listed and tabulated by system organ class, preferred term, and treatment. Clinical laboratory test results will be listed and summarized by treatment. Any significant PE (full or targeted) findings, and clinical laboratory results will be listed. Vital sign measurements will be listed. ECG readings (reviewed by a central laboratory) will be evaluated by the investigator and abnormalities, if present, will be listed.

For subjects with serial ECG measurements and time-matched PK, $\Delta QTcF$, ECG intervals QRS and PR, and in heart rate will be tabulated by dose and study day. Frequency distributions of maximum QTcF values, maximum $\Delta QTcF$, maximum QRS, maximum PR interval, and maximum heart rate in prespecified categories will be tabulated by dose. Scatter plots of heart rate, change in heart rate, QTc, and $\Delta QTcF$ vs time-matched active ADC and unconjugated tubulysin concentrations will be provided. A concentration-response effect of BMS-986183 as monotherapy on QTcF may be assessed by a linear mixed effects regression model for $\Delta QTcF$ on plasma and serum concentrations, stratified by study day, as well as pooled across days. Additional modeling of exposure-response may also be explored.

8.4.4 Pharmacokinetic Analyses

PK parameters for the total antibody, active ADC, conjugated tubulysin, and unconjugated tubulysin will be calculated using noncompartmental analysis.

PK analysis will be provided separately for each of the above analytes. Summary statistics will be tabulated for the PK parameters by dose, dose regimen, and study day for each select analyte. To describe the dependency on dose, scatter plots of Cmax and AUC(TAU) vs dose will be provided, on indicated study days for each dose regimen. In addition, exploratory assessment of dose proportionality will be based on a power model and a CI around the power will be calculated. To assess the attainment of steady-state geometric mean trough observed concentration values will be plotted vs study day by dose and dose regimen.

Associations between PK and select safety and efficacy measures may be explored.

PPK and exposure-response analyses for BMS-986183 and for nivolumab may be conducted, which would be presented in a separate report.

